Influence of Custom Orthosis Post Carpometacarpal (CMC) Arthroplasty

NCT050307510

Document date: document created for submission to UToledo IRB. Approval date of IRB 2/21/22.

THE ELEMENTS OF A RESEARCH PROTOCOL

Influence of custom orthosis post CMC arthroplasty

1. Background, Review of the Literature, Significance

Carpometacarpal (CMC) osteoarthritis (OA) can cause severe pain and loss of hand function, thumb motion and thumb strength (Fontana et al., 2007). CMC arthroplasty, surgery on the thumb joint, is conducted when conservative treatments for CMC OA fail (Grenier et al. 2016). In 2011, 6,960 CMC arthroplasties were conducted in the United States (Werner et al., 2015). Splints or orthoses are typically used after surgery to immobilize the joint as the wound heals. Previous studies have reported mixed results in the comparison of outcomes related to use of custom orthoses and prefabricated splints (Baradaran et al., 2018; Sillem et al., 2011; Marotta et al., 2020; Bani et al., 2013). This study aims to compare post-surgical outcomes, including wound dehiscence, pain, function, and satisfaction with device and care from individuals who receive either a custom orthosis or prefabricated splint after CMC arthroplasty. This study will allow for increased understanding about the pros and cons of prefabricated splints versus custom orthosis which can inform clinical decisions in order to decrease wound dehiscence, the pain associated with wound dehiscence, and enhance function post-surgery for individuals who have CMC arthroplasty.

2. Objectives/Specific Aims

- To determine the difference in the incidence of wound dehiscence after a CMC arthroplasty when using a custom orthosis as compared to a prefabricated splint.
- To determine the difference in subject reported pain levels after a CMC arthroplasty between those who received a custom orthosis as compared to those who received a prefabricated splint.
- To determine the difference in function as measured by the QuickDASH, active range of motion measurements of the thumb, and subtests within the applied dexterity section of the Arthritis Hand Function Test (AHFT) between those wearing a custom orthosis as compared to those wearing a prefabricated splint.
- To determine the difference in subject satisfaction with device and services at the first and second post-operative appointment.

3. Methods

a) **Study Design**

- Experimental, two groups with random assignment

b) **Method of treatment assignment**

Subjects will be randomly assigned using at the initial follow-up appointment following CMC arthroplasty. The surgeon may exclude the subject, following assessment, if the subject cannot be randomly assigned to an intervention group. Open-label blinding will be used since every member of the team will be able to perceive whether the subject has

received a custom orthosis or prefabricated splint. Random assignment to the two groups will be completed in SPSS.

c) Inclusion/exclusion criteria

Inclusion criteria for subjects include status post CMC arthroplasty (within 4-5 weeks), 18 or older, able to read and understand English, capable of independently consenting to health care procedures.

Subjects will be excluded from the study if the surgeon identifies risk factors that would preclude random assignment to the control or experimental group. Subjects will also be excluded if they request a prefabricated or custom orthosis.

d) Justification of the number of subjects

Anticipated number of subjects that will be requested for enrollment is 125 subjects. A sample size of at least 96 is required for a power of 60 with $\alpha = .05$.

e) Study setting

University of Toledo Medical Center (UTMC) outpatient.

f) Primary and secondary outcome measures

Primary Outcomes include:

Function - as measured by the QuickDASH

Wound dehiscence – as measured by the Sandy Grading System

Pain - as measured by the Visual Analog Pain Scale

Thumb CMC Active Range of Motion (AROM) measurements

Subtests within the applied dexterity section of the Arthritis Hand Function Test

Satisfaction with device and services – as measured by the OPUS.

Secondary variables of interest include:

Demographic data such as age, gender, race, handedness, pre-existing conditions current medications and supplements, smoking history, and alcohol consumption.

h) Procedures, interventions, schedule

FIRST POST-OP APPOINTMENT

Standard of care: At the initial post-op appointment with the surgeon, the client will check in and register for the appointment. A member of the surgical team will assess the client and document the Sandy Score.

Research specific: As a member of the surgical team assesses the client he/she will determine if the client meets the inclusion criteria. If the client does meet the inclusion criteria, the study will be briefly explained using the recruitment flyer. The client will then be asked if he/she is interested in participating.

If the client is interested in participating, a member of research team will meet with the client to review the consent form and answer any questions. Once any questions have been answered, if the subject agrees to participate, he/she will sign the informed consent form. The subjects will be informed both verbally and in writing that they can take consent away at any

time during the research study. A copy of the informed consent form will be given to the subject. The client will be randomly assigned to intervention A or intervention B.

Standard of Care: The subject will receive either a prefabricated splint (Intervention A) or custom orthosis (Intervention B).

Research specific: The subject will then be asked to complete the demographic questionnaire, QuickDASH, and the Pain VAS. Thumb CMC active range of motion measurements will then be collected (radial and palmar abduction). Participants will also complete subtests within the applied dexterity section of the Arthritis Hand Function Test and OPUS survey.

Subjects who are assigned to Intervention A (the prefabricated splint group) will be provided a splint by a member of the surgical team. Subjects who are assigned to Intervention B (the custom orthosis group) will be evaluated by an occupational therapist and a custom orthosis will be fabricated.

SECOND POST-OP APPOINTMENT

Standard of Care: Approximately 4-5 weeks later, subjects will attend a second post-op appointment and be assessed by a member of the surgical team. The Sandy score will be documented.

Research specific: At this time, a member of the research team will ask the subject to complete the, QuickDASH, and the Pain VAS. Thumb CMC active range of motion measurements will then be collected (radial and palmar abduction). Participants will also complete subtests within the applied dexterity section of the Arthritis Hand Function Test and OPUS survey.

i) Planned data analysis

Means and standard deviations will be calculated for the demographic information such as age and alcohol consumption per week. In-group and between-group percentages will also be calculated for demographic information, such as gender, pre-existing diabetes, and smoking history. The means and standard deviations of scores received on the QuickDASH, Sandy Grading System, Pain VAS, and AROM will be calculated. In-group and between-group descriptive statistics will be calculated for scores on the OPUS and Applied Dexterity section of the Arthritis Hand Function test. Independent student t-tests will be conducted to compare the means between Interventions A and B. Dependent student t-tests will be conducted to compare the initial post-op assessment mean data to the second post-op assessment mean data within groups. P-values will be considered significant if they are less than or equal to 0.05.

4. Reference List

Baca, M. E., Rozental, T. D., McFarlane, K., Hall, M. J., Ostergaard, P. J., & Harper, C. M. (2020). Trapeziometacarpal joint arthritis: is duration of symptoms a predictor of

surgical outcomes? *The Journal of Hand Surgery*, 45(12), 1184.e1-1184.e7. <https://doi.org/10.1016/j.jhsa.2020.05.026>

Bani, M. A., Arazpour, M., Kashani, R. V., Mousavi, M. E., & Hutchins, S. W. (2013). Comparison of custom-made and prefabricated neoprene splinting in patients with the first carpometacarpal joint osteoarthritis. *Disability & Rehabilitation: Assistive Technology*, 8(3), 232–237. <https://doi.org/10.3109/17483107.2012.699992>

Bani, M. A., Arazpour, M., Kashani, R. V., Mousavi, M. E., Maleki, M., & Hutchins, S. W. (2013). The effect of custom-made splints in patients with the first carpometacarpal joint osteoarthritis. *Prosthetics and Orthotics International*, 37(2), 139–144. <https://doi.org/10.1177/0309364612454047>

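### Aim 1 asks for incidence of dehiscence under each device, but the Sandy comparison does not separate wounds already dehisced before the device from new ones

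*Combined protocol and SAP*

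**What the plan says.** All references are to the combined protocol and SAP.

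- **Aim 1 (section 2):** "To determine the difference in the incidence of wound dehiscence after a CMC arthroplasty when using a custom orthosis as compared to a prefabricated splint".
- **Entry (3.c):** "Inclusion criteria for subjects include status post CMC arthroplasty (within 4-5 weeks), 18 or older, able to read and understand English", plus capacity to consent. No criterion mentions the wound.
- **Exclusion (3.c):** "Subjects will be excluded from the study if the surgeon identifies risk factors that would preclude random assignment to the control or experimental group". Section 3.b adds that the surgeon may make this exclusion after assessing the subject. Dehiscence is not named in either place.
- **Visit 1 (3.h):** "A member of the surgical team will assess the client and document the Sandy Score". Consent follows, then "The client will be randomly assigned to intervention A or intervention B", then the device is supplied.
- **Visit 2 (3.h):** "Approximately 4-5 weeks later, subjects will attend a second post-op appointment and be assessed by a member of the surgical team", with a second Sandy score.
- **Analysis (3.i):** "The means and standard deviations of scores received on the QuickDASH, Sandy Grading System, Pain VAS, and AROM will be calculated". Arms are compared by independent t-test, and the visit is not stated. Visits are compared within each arm by paired t-test.

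**The concern.** Incidence while using a device means dehiscence that begins after the device is supplied. Here the device starts at the first post-operative visit, and 3.c allows that visit to fall up to 4-5 weeks after surgery. A wound may already have opened by then. The plan records this, but makes no use of it when the arms are compared.

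A wound open before assignment and still open at visit 2 therefore enters the same arm mean as a wound that opened under the study device. At stake is whether the Aim 1 result answers the question asked. There may also be a loss of contrast and precision, in a trial whose stated power is only 60.

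**Working it through.** **Inputs.** From 3.h: the order at visit 1 is Sandy score, consent, assignment, device, and one further Sandy score follows about 4-5 weeks later. From 3.d: at least 96 subjects for a power of 60 at alpha .05. Not given: any dehiscence rate, the share dehisced at visit 1, the Sandy grade definitions, the allocation ratio, and the outcome, test and effect size behind 96.

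**The plan's own figure.** The 96 cannot be reproduced without an effect size. With 48 per arm (1:1 assumed), 60% power and a two-sided 5% test, it fits 5% vs 19.9%, 10% vs 27.6%, or a standardised mean difference of about 0.45. None of these is stated, so 96 serves below only as a scale.

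**Does the planned analysis yield incidence?**

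| Planned step | Uses visit-1 score? | Compares arms? |
|---|---|---|
| Mean and SD of Sandy score | Descriptive only | No test |
| Independent t-test | No restriction or adjustment | Yes |
| Paired t-test within arm | Yes | No |

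No step does both, and none defines a new event.

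**Formula.** Let q be the share dehisced at visit 1, s the share of those still dehisced at visit 2, and p the new dehiscence among wounds intact at visit 1. C is custom and P is prefabricated.

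- Share dehisced at visit 2 = q·s + (1 − q)·p
- Difference, P minus C = q(sP − sC) + (1 − q)(pP − pC)

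If s is equal in both arms, the difference is (1 − q) times the true one. The same decomposition holds for mean grade, with group means in place of s and p. The document gives nothing from which to put numbers on grades, so proportions are used as an illustration.

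**Illustration 1.** Assumed: pC = 5%, pP = 10%, and equal s in both arms. True risk ratio 0.50, true difference 5 points.

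| q | All persist (s = 1) | Half persist (s = 0.5) | All heal (s = 0) | Difference (any s) |
|---|---|---|---|---|
| 5% | 9.75% vs 14.5%, ratio 0.67 | 7.25% vs 12.0%, ratio 0.60 | 4.75% vs 9.5%, ratio 0.50 | 4.75 points |
| 10% | 14.5% vs 19.0%, ratio 0.76 | 9.5% vs 14.0%, ratio 0.68 | 4.5% vs 9.0%, ratio 0.50 | 4.5 points |
| 20% | 24.0% vs 28.0%, ratio 0.86 | 14.0% vs 18.0%, ratio 0.78 | 4.0% vs 8.0%, ratio 0.50 | 4.0 points |

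Example: q = 10%, s = 1 gives 0.10 + 0.90 × 0.05 = 0.145 and 0.10 + 0.90 × 0.10 = 0.190.

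**When dilution fails.** Keep q = 10% and the same p, but let persistence differ.

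- sC = 75%, sP = 80%: 0.075 + 0.045 = 0.120 vs 0.080 + 0.090 = 0.170. The difference is still 5 points.
- sC = 50%, sP = 100%: 0.050 + 0.045 = 0.095 vs 0.100 + 0.090 = 0.190. The difference grows to 9.5 points.

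On the difference scale, dilution requires sP − sC to be smaller than pP − pC.

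**Illustration 2, power.** Assumed: new dehiscence 5% vs 20%, equal s, 48 per arm, normal-approximation two-sided 5% test of two proportions. With q = 0 the power is 60.6%, in line with 3.d.

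| q | Everyone, all persist | Everyone, half persist | Intact at visit 1 only (expected n per arm) |
|---|---|---|---|
| 5% | 46% | 51% | 58% (45.6) |
| 10% | 36% | 43% | 56% (43.2) |
| 20% | 25% | 31% | 51% (38.4) |

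Under these assumptions, the smaller denominator costs less power than the mixing does.

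**Chance imbalance.** At q = 10% and 48 per arm, the between-arm difference in the share already dehisced has standard deviation √(2 × 0.10 × 0.90 / 48) = 0.061, about 6 points. That exceeds the 5-point effect of illustration 1, and no adjustment is planned.

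**The case against.** Several points on the other side are sound.

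- **The plan tests mean grade.** It contains no proportion or risk ratio for the Sandy score, so the ratios above are not forecasts of this trial's result. This stands. It also exposes the more basic gap, that Aim 1 has no defined event.
- **Dilution is conditional.** A reader might infer that the device effect is certainly diluted. The document does not support that. The visit-2 score also reflects persistence and severity of older wounds, which the device might change, and the working shows cases with no dilution or the reverse.
- **Persistence and prevalence are assumed.** If few wounds are open at visit 1 the matter is small. If all heal by visit 2, the ratio is untouched and only the absolute difference shrinks.
- **The surgeon can exclude after assessment.** That decision is made with wound status known and may lower q. It is discretionary and names no wound criterion, so it does not rule such cases out.
- **Randomisation balances older wounds in expectation.** Correct. A reader might suspect systematic bias toward one device; nothing in the document supports that.
- **Broad entry is a legitimate choice.** Also correct. A reader might conclude that 3.c is wrong, but the gap lies in how the outcome is defined and analysed.

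None of this turns the visit-2 comparison into incidence under the device.

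**Conclusion.** The point holds in a limited form. Followed exactly, the plan does not deliver the incidence named in Aim 1: subjects dehisced before the device may be enrolled, and the only test that uses their visit-1 score does not compare the arms. This rests on the text alone and needs no assumed rate.

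Loss of contrast and added noise are possible consequences, not established ones. They depend on some subjects being dehisced at visit 1 and, for dilution, on the device affecting existing wounds less than it affects new dehiscence. Their size cannot be derived from the document. Across the ranges in illustration 1, a true risk ratio of 0.50 would appear anywhere from 0.50 to 0.86. The absolute difference would shrink by 5% to 20% of its true value.

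**What to change.** Change 3.f and 3.i, and leave eligibility as it is.

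1. In 3.f, define the Aim 1 outcome as new dehiscence at visit 2: a yes/no event with a stated Sandy cut-off. The document does not define the grades, so the sponsor must supply the cut-off.
2. In 3.i, compare the proportion with that event between arms among randomised subjects whose visit-1 Sandy score shows no dehiscence. That score precedes assignment, so the restriction keeps the randomised comparison intact.
3. Report subjects dehisced at visit 1 separately by arm, as healed, unchanged or worse, and keep them in the other aims.
4. If mean Sandy grade is also compared between arms, name the visit and adjust for the visit-1 grade.

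The cost is wording only, since both scores are already collected. The downside is a somewhat smaller Aim 1 denominator: at an assumed 10% already dehisced, about 43 of 48 per arm. The Aim 1 result would then apply to wounds intact when the device is supplied, and the report should say so.

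### Time since surgery at visit 2 is loosely fixed and the between-arm t-tests use neither it nor the visit-1 score: a small, nearly free gain in precision is left out, with no bias

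*Combined protocol and SAP*

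**What the plan says.** Section 3, item c (Inclusion/exclusion criteria) requires "status post CMC arthroplasty (within 4-5 weeks". This is the only statement of entry time relative to surgery, and it has no lower limit.

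Section 3, item b (Method of treatment assignment) places randomisation "at the initial follow-up appointment following CMC arthroplasty". The week of that appointment is not given.

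Section 3, item h (Procedures) times the final assessment from the first visit, not from surgery: "Approximately 4-5 weeks later, subjects will attend a second post-op appointment".

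Section 3, item i (Planned data analysis) compares arms without covariates: "Independent student t-tests will be conducted to compare the means between Interventions A and B". Change over time is tested separately within each arm by paired t-tests.

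The secondary variables in item f are "Demographic data such as age, gender, race, handedness, pre-existing conditions current medications and supplements, smoking history, and alcohol consumption". Time since surgery is not among these examples.

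On sample size, item d says "A sample size of at least 96 is required for a power of 60".

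**The concern.** Function, pain, thumb motion and dexterity are measured while subjects recover from an operation. If these scores change with time since surgery, subjects seen at different stages differ for a reason unrelated to the device. Randomisation balances stage between arms on average. An unadjusted t-test still carries the spread in its error term, and makes no use of a chance imbalance that could be seen and corrected. The visit-1 score, which is already collected, is also left out of the between-arm test.

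What is at stake is precision. The stated power of 60, read as 60%, leaves little to spare. A reader also cannot tell from the two 4-5 week statements how long after surgery the final outcomes are taken.

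**Working it through.** **Timing permitted by the text.** With no lower limit, visit 2 falls between 0 + 4 = 4 and 5 + 5 = 10 weeks after surgery. If the criterion means that entry occurs 4-5 weeks after surgery, the range is 4 + 4 = 8 to 5 + 5 = 10 weeks.

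**The plan's own figure.** The required 96 cannot be reproduced, because no effect size, SD, event rate or endpoint is given. Working backwards with 48 per arm (1:1 assumed), two-sided 0.05 (sidedness assumed) and 60% power gives a standardised difference of d = 0.456 by the t-test. The noncentrality is 0.456 × √(48/2) = 2.236.

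**Model and assumptions (none from the documents).** T1 is weeks from surgery to visit 1, uniform over the stated entry range. The gap to visit 2 is uniform over 4-5 weeks, with variance 1/12. Scores change linearly by b SD per week, with residual SD 1. The effect is scaled so that the unadjusted test always has 60% power.

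**Adjusting for days from surgery to visit 1 alone.**

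R² = b²Var(T1) / [1 + b²(Var(T1) + 1/12)]. Power comes from the noncentral t with noncentrality 2.236/√(1 − R²) and 93 df.

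Example, entry over 0-5 weeks and b = 0.2: Var(T1) = 25/12 = 2.083; R² = 0.0833/1.0867 = 0.077; noncentrality 2.236/√0.923 = 2.327; power 63.4%.

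| Entry range (Var T1) | b = 0.1 | b = 0.2 | b = 0.3 |
|---|---|---|---|
| 0-5 weeks (25/12) | R² 2.0%, power 60.9% | 7.7%, 63.4% | 15.7%, 67.4% |
| 1-3 weeks (4/12) | 0.3%, 60.1% | 1.3%, 60.6% | 2.9%, 61.3% |
| 4-5 weeks (1/12) | 0.1%, 60.0% | 0.3%, 60.1% | 0.7%, 60.3% |

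**Adding the visit-1 score.** Assume the same slope at both visits and a residual correlation ρ between visits. Let v1 = 1 + b²Var(T1), v2 = v1 + b²/12 and c = ρ + b²Var(T1).

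- Visit-1 score alone: R² = c²/(v1·v2).
- Visit-1 score and days: R² = 1 − (1 + b²/12 − ρ²)/v2, with 92 df.

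Example, entry over 0-5 weeks, b = 0.1, ρ = 0.5: v1 = 1.0208, v2 = 1.0217, c = 0.5208. The visit-1 score alone gives R² = 0.260 and power 73.0%. With days added, R² = 0.265 and power 73.3%.

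| ρ (entry 0-5 weeks) | Power with visit-1 score, b = 0.1 to 0.3 | Points added by days since surgery |
|---|---|---|
| 0.3 | 64% to 68% | 0.5 to 3.5 |
| 0.5 | 73% to 77% | 0.3 to 2.0 |
| 0.7 | 88% to 91% | 0.1 to 0.7 |

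With entry over 1-3 weeks, days add at most 0.7 points (ρ = 0.3, b = 0.3). With entry at 4-5 weeks they add less than 0.2.

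**Validity of the t-test.** In 4,000 simulated null trials per slope (b = 0 to 0.3, entry over 0-5 weeks, 48 per arm), the unadjusted t-test rejected 4.75% to 5.1% of the time. The Monte Carlo standard error is √(0.05 × 0.95/4,000) = 0.34 points, so this agrees with 5%.

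**The case against.** The strongest objection is that nothing is wrong with the t-test. Randomisation protects the comparison and type I error is held, so choosing a covariate model is an efficiency preference. This stands: the point is about precision only. A reader might infer that uneven timing biases the comparison between devices. Neither the documents nor the simulation supports that.

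A second objection is that 4 to 10 weeks is only an outer limit. A reader might infer that subjects enter at any time during the first five weeks, so that outcomes really are spread over that range. The documents do not support this either. Each subject enters at one initial post-operative visit with the surgeon, in one outpatient setting, and such visits may cluster. The 67% figure needs both the widest entry spread and the steepest slope assumed here.

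A third objection is that the visit-1 score already carries much of the recovery-stage information. This largely stands. Only with the widest spread, steepest slope and weakest correlation are the two covariates about equally useful (67.4% for days alone, 67.9% for the visit-1 score alone).

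A fourth objection is that the visit-1 score may not be a safe covariate. This also stands, as a condition on the fix. Item h puts random assignment and receipt of the device before the visit-1 questionnaires, then describes device provision again after them. In an open-label trial, a score taken once the assignment is known or the device is on could reflect the arm, and adjusting for it could remove part of the effect. Days from surgery to visit 1 is fixed before randomisation and has no such problem.

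**Conclusion.** The point holds as a minor improvement. The plan leaves the timing of visit 2 relative to surgery unclear and compares arms without two variables that cost almost nothing to use. The gain from time since surgery alone ranges from almost nothing to about 7 power points on a base of 60%. It is about 0 to 3.5 points once the visit-1 score is in the model. The visit-1 score is the more useful covariate in most scenarios, provided that it is a true pre-assignment measurement.

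These sizes rest on assumed slopes, entry spreads and correlations, on 1:1 allocation and two-sided testing, and on reading the stated power as 60%. The timing arithmetic, the missing lower limit and the absence of covariates come directly from the text.

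**What to change.** In section 3, item i, for each continuous outcome at visit 2, replace the unadjusted between-arm t-test with a linear model containing arm, days from surgery to visit 1, and the visit-1 value. Use the visit-1 value only where it is measured before the assignment is known and the device is fitted. Otherwise use arm and days alone. The two descriptions of the order of events at the first visit in item h must be reconciled first. A visit-1 rating of satisfaction with the assigned device cannot meet this condition.

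Report days since surgery at both visits by arm. Reconcile the 4-5 week statements in items c and h so that it is clear what each is measured from. No clinical window is proposed here.

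The cost is analysis wording and one recorded variable, which must already be known to check eligibility. Each covariate uses one degree of freedom of about 94. No new visit or procedure is needed.

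### Section 3(d) gives 96 subjects a 60% power with no outcome or effect attached; for the dehiscence aim, power to detect an assumed halving from 10% or 20% is below 30% at that size, and section 3(i) never estimates incidence

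*Combined protocol and SAP*

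**What the plan says.** Section 3(d) has two sentences. The first gives the recruitment figure: "Anticipated number of subjects that will be requested for enrollment is 125 subjects". The second is "A sample size of at least 96 is required for a power of 60", with alpha set at .05. It does not say which outcome, effect size, standard deviation, event rate, test or sidedness lies behind the 96. Nor does it say whether 96 is a total or a per-arm number, or whether it counts subjects with second-visit data.

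Section 3(f), under "Primary Outcomes include", lists six measures: QuickDASH, dehiscence by Sandy grade, pain VAS, thumb motion, dexterity subtests and OPUS satisfaction. The first aim in section 2 is "To determine the difference in the incidence of wound dehiscence after a CMC arthroplasty", comparing the two devices.

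On allocation, section 3(b) says "Random assignment to the two groups will be completed in SPSS" and gives no ratio. On analysis, section 3(i) says "The means and standard deviations of scores received on the QuickDASH, Sandy Grading System, Pain VAS, and AROM will be calculated" and then "Independent student t-tests will be conducted to compare the means between Interventions A and B". Its only inferential rule is "P-values will be considered significant if they are less than or equal to 0.05". No proportion with dehiscence, test of proportions or confidence interval is planned.

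**The concern.** A power figure means something only together with an outcome and an effect. With six primary outcomes and one unattached figure, a reader can apply the 60% to any of them, including dehiscence. Dehiscence is the first aim and, as an incidence, is binary. Binary outcomes carry less information per subject than continuous scores, so a sample that gives 60% for a moderate difference on a score can give far less for a plausible difference in rates.

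Section 1 says the results are meant to inform the choice of device so as to reduce dehiscence. If the dehiscence comparison is non-significant and the reader believes it had 60% power, the result will look more informative than it is. The planned analysis supplies no interval to correct that impression, and a mean Sandy grade is not an incidence.

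**Working it through.** **Inputs from the protocol.** N = 96 and power 60, read as 60% (3(d)); alpha 0.05 (3(d), 3(i)); independent t-test (3(i)); 125 to be requested (3(d)).

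**Assumptions, because the protocol is silent.** 96 is the total; allocation is 1:1, so 48 per arm; tests are two-sided; the prefabricated-arm dehiscence rate is 10% or 20% and is halved in the custom arm.

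**Step 1: the plan's own figure.** It cannot be reproduced forwards, because no effect is given. Solved backwards with the normal formula, d = (z₀.₉₇₅ + z_power) × √(2/n):

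- 60% power: (1.960 + 0.253) × √(2/48) = 2.213 × 0.2041 = 0.452 SD.
- 80% power: (1.960 + 0.842) × 0.2041 = 0.572 SD.

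The noncentral t gives 0.456 and 0.578 SD. With all 125 analysed (62.5 per arm) it gives 0.399 and 0.505 SD.

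These values depend on the assumptions. The same sentence gives 0.39 SD if the test is one-sided, 0.32 SD if 96 is per arm, and 0.33 SD for a paired test within one arm of 48.

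**Step 2: dehiscence at 48 per arm.** Every pair of event counts was enumerated from two binomial distributions, and the probabilities of the pairs with p ≤ 0.05 were summed.

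| Prefabricated vs custom (assumed) | t-test on 0/1 | Uncorrected chi-square | Fisher exact |
|---|---|---|---|
| 10% vs 5% | 14% | 17% | 6% |
| 20% vs 10% | 29% | 29% | 18% |
| 20% vs 5% | 64% | 66% | 48% |
| 40% vs 20% | 57% | 59% | 49% |

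Check by the pooled-z formula for 20% vs 10%: the pooled rate is 0.15, so SE₀ = √(2 × 0.15 × 0.85/48) = 0.0729 and SE₁ = √((0.16 + 0.09)/48) = 0.0722. Power = Φ((0.10 − 1.96 × 0.0729)/0.0722) = Φ(−0.59) = 28%. For 10% vs 5% the same formula gives 15%.

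The t-test on 0/1 is the closest match to the planned test. Power for the mean Sandy grade itself cannot be computed, because no grade distribution is given.

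**Step 3: dehiscence at 125.** The odd subject can fall in either arm. For 10% vs 5%, power is 10-14% (Fisher) or 16-20% (chi-square or t). For 20% vs 10%, it is 27-32% (Fisher) or 35% (chi-square or t). The overall range is about 10-35%.

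**Step 4: what an interval would show.** The approximate 95% half-width for a difference in proportions at 48 per arm is 1.96 × √((p₁(1−p₁) + p₂(1−p₂))/48). For 10% vs 5% this is 1.96 × √(0.1375/48) = 0.105. For 20% vs 10% it is 1.96 × √(0.25/48) = 0.141. The observed differences would be 5 and 10 percentage points, with intervals of about ±10.5 and ±14.1 points. Reporting them would show the imprecision directly.

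**The case against.** The strongest reply is that no miscalculation has been shown. The 96 is uncheckable, not wrong, and the protocol openly states a modest power. That stands: this is an incomplete statement, not an arithmetic error.

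A reader might go further and infer that 96 subjects at 60% power fix a single effect size of 0.46 SD. They do not. That value needs four unstated conditions (96 in total, 1:1, two-sided, independent t-test). Nor can one say that no standard calculation yields 96: a chi-square test with effect size w = 0.3 and 5 degrees of freedom reaches 60% at N = 95.5. Nothing in the protocol says this was the source.

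A reader might also infer that 60% power is impossible for dehiscence. The documents do not support that either, since they give no incidence. A fall from 20% to 5% has 66% power by chi-square at 96 subjects. Likewise, it would be wrong to say that no halving ever reaches 60%: with 125 subjects, 40% vs 20% has 65-70%.

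Finally, the protocol nowhere claims equivalence or says it will treat non-significance as no difference. That is right. The risk is one of interpretation, left open by the combination of an unattached power figure and a bare p-value rule.

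**Conclusion.** The point holds in conditional form. The 60% in section 3(d) has no outcome, effect, test or sidedness and cannot be read as the power of a trial with six primary outcomes. On the usual reading (96 in total, 1:1, two-sided t-test) it describes a difference of about 0.46 SD on one continuous score.

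For the dehiscence aim, if the prefabricated-arm rate is 10-20% and the custom orthosis halves it, every test examined has power below 30% at 96 subjects. A real halving would therefore be missed at least about 70% of the time. With 125 analysed, power is still no more than about 35%. These rates are assumptions; at 96 subjects, larger absolute differences are needed to come near 60%.

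Separately, and without any assumption about rates, section 3(i) as written would not estimate the quantity that the first aim names.

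**What to change.** In section 3(d), replace the power sentence with one to this effect: *With 96 subjects who have second-visit data (48 per arm, two-sided alpha 0.05), a between-arm t-test on one continuous outcome has 60% power for a difference of 0.46 SD. At this sample size, power to detect a halving of wound dehiscence from an assumed 10-20% is below 30%.* If the sponsor holds a different calculation behind the 96, give its outcome, effect and test instead, and keep the dehiscence sentence.

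In section 3(i), add: *Aim 1 will be reported as the difference between arms in the proportion of subjects with dehiscence, with its 95% confidence interval. A non-significant p-value will not be read as evidence of no difference.*

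The cost is a less favourable stated power for the first aim and a small amount of extra analysis on Sandy scores that are already collected. No additional subjects, visits or measurements are needed.
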